10.2 All-location, all-cause 28-day mortality

All location, all cause 28-day mortality is defined as death between randomization and 28 days after randomization from any cause and in any location, including after discharge from the index hospitalization. Data on death will be collected from the electronic health record during the hospitalization and then from telephone calls to the patient or surrogate after discharge on Study Day 8, 15 and 29.

10.3 Survival through 28 days

Vital status will be recorded between randomization and 28 days following randomization using in-hospital data and follow-up calls post-discharge on Study Day 8, 15, and 29.

10.4 Hospital discharge through 28 days

The count of days after randomization until discharge from the index hospitalization occurs, or day 28, whichever is longer, will be recorded. Death will be treated as a competing risk.

10.5 Time to Recovery

Recovery is defined as reaching category 1, 2, or 3 on the seven-category COVID Ordinal Outcome Scale. A patient can reach category 1, 2, or 3 on the seven-category COVID Ordinal Outcome Scale either by (a) being discharged from the hospital or by (b) being liberated from supplemental oxygen for the final time during the index hospitalization. Time to recovery is defined as the time between randomization and the first of either hospital discharge or liberation from supplemental oxygen for the final time during the index hospitalization. Time to recovery is an “in-hospital outcome” and does not reflect information on receipt of supplemental oxygen, rehospitalization, or death after discharge from the index hospitalization.⁷

For a patient who is not receiving supplemental oxygen at the time of randomization, and who never receives supplemental oxygen during the index hospitalization, the time to recovery is 0.0 days. For a patient who receives supplemental oxygen at any time between randomization and discharge from the index hospitalization, but who is not receiving supplemental oxygen at the time of discharge from the index hospitalization, the time to recovery is the time from randomization to the time of final receipt of supplemental oxygen during the index hospitalization. For a patient who is receiving supplemental oxygen at the time of discharge from the index hospitalization, the time to recovery is the time from randomization to the time of discharge from the index hospitalization. Patients who remain hospitalized and receiving supplemental oxygen 28 days after randomization are not considered to have experienced recovery. All patients who die prior to discharge from the index hospitalization are not considered to have experienced recovery. Patients who do not experience recovery will be awarded a value for the outcome of time to recovery of 28.0 days.

10.6 COVID Ordinal Outcomes Scale on Study Day 3

This outcome is defined as clinical status 2 days after randomization (measured on Study Day 3) as assessed with the seven-category COVID Ordinal Outcome Scale, as described in the section on the Primary Outcome. Data on clinical status is collected from the electronic health record during the hospitalization. Patients discharge prior to Study Day 3 will have the Day 3 COVID Ordinal Outcome Scale coded as level 2 (not hospitalized with limitation in activity).

10.7 COVID Ordinal Outcomes Scale on Study Day 8

This outcome is defined as clinical status 7 days after randomization (measured on Study Day 8) as assessed with the seven-category COVID Ordinal Outcome Scale, as described in the section on the Primary Outcome. Data on clinical status is collected from the electronic health record during the hospitalization and then from telephone calls to the patient or surrogate after discharge from the index hospitalization.

10.8 COVID Ordinal Outcomes Scale on Study Day 29

This outcome is defined as clinical status 28 days after randomization (measured on Study Day 29) as assessed with the seven-category COVID Ordinal Outcome Scale, as described in the section on the Primary Outcome. Data on clinical status were collected from the electronic health record during the hospitalization and then from telephone calls to the patient or surrogate after discharge from the index

hospitalization. Missing data for the COVID Ordinal Outcomes Scale on Day 29 will be handled in the same fashion as described for the primary outcome.

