6.1 Primary Outcome

COVID-19 7-point Ordinal Clinical Progression Outcomes Scale on Study Day 15:

1. Not hospitalized with resumption of normal activities.
2. Not hospitalized, but unable to resume normal activities.
3. Hospitalized, not on supplemental oxygen.
4. Hospitalized, on supplemental oxygen.
5. Hospitalized, on nasal high-flow oxygen therapy, noninvasive mechanical ventilation, or both
6. Hospitalized, on ECMO, invasive mechanical ventilation, or both.
7. Death

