7.3 Assessments Following Hospital Discharge

7.3.1 Acute Care Follow-up

For participants discharged to home or a post-acute care facility (e.g., long term acute care facilities, skilled nursing facilities, or acute rehabilitation facilities) prior to the Day 8, Day 15 or Day 29 assessment, we will perform these assessments via telephone follow-up. The Day 8 call window will be Day 8 through 14. The Day 15 call window will be Day 15 through 22. The Day 29 call window will be Day 29 through 36. During these telephone calls, we will interview the patient, LAR, or facility staff to assess:

- Date of death (if applicable)
- ED visits and hospital readmissions after hospital discharge
- Location at the time of the call (home, long term acute care facility, skilled nursing facility, acute rehabilitation facility, hospital)
- Selected non-laboratory safety outcomes after hospital discharge
- COVID-19 7-point Ordinal Clinical Progression Outcomes Scale

The follow-up period for vital status (dead versus alive) is through Study Day 29. For most patients, we will establish vital status during the Study Day 29 visit (either in person for those who remain in the hospital or by phone for those who have been discharged). For patients who are not reached for the Study Day 29 visit, we will seek to establish vital status via phone calls, emails, and searches through medical records, obituaries, social media, and other sources.

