For calculation of oxygen-free days, supplemental oxygen is defined as oxygen administered by nasal cannula, face mask, high-flow nasal cannula, non-invasive ventilation, or invasive ventilation. Positive airway pressure (CPAP, BiPAP) provided solely at night as treatment for sleep-disordered breathing (e.g. obstructive sleep apnea) is not considered supplemental oxygen. Oxygen-free days are calculated as the number of whole calendar days alive and not receiving supplemental oxygen between randomization and study day 29. Patients who die before Day 29 receive a value of 0. If a patient survives through study day 29 and never receives supplemental oxygen, the number of oxygen-free days is 28. If a patient receives supplemental oxygen and survives through study day 28, the number of oxygen free-days is calculated as 28 minus the number of calendar days from the first day on which the patient receives supplemental oxygen until the last day on which the patient receives supplemental oxygen. Days on which the patient does not receive supplemental oxygen that occur between days on which the patient receives supplemental oxygen do not count towards the number of oxygen free days. Data on oxygen use are censored at hospital discharge and the last observed status will be carried forward (“in-hospital outcome”). That is, if the patient is receiving supplemental oxygen at hospital discharge, the analysis assumes they continue to receive supplemental oxygen through Study Day 29. If the patient is not receiving supplemental oxygen at hospital discharge, the analysis assumes the patient continues not to receive supplemental oxygen through Study Day 29.

10.9.2 Ventilator-free days to Day 28

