Ventilator-free days to day 28 is defined as the number of whole calendar days alive and breathing without invasive mechanical ventilation from 00:00 on the day of randomization through Study Day 29. Patients who die before Study Day 29 receive a value of 0. If a patient survives to the first of discharge or Study Day 29 and never receives invasive mechanical ventilation, the number of VFDs is 28. If a patient receives invasive mechanical ventilation and survives to the first of hospital discharge or Study Day 28, the number of VFDs is calculated as 28 minus the number of calendar days from the first day on which the patient received invasive mechanical ventilation until the last day on which the patient received invasive mechanical ventilation. Days on which the patient does not receive invasive mechanical ventilation that occur between days on which the patient did receive mechanical ventilation do not count towards the number of VFDs. Data on ventilation are censored at hospital discharge and the last observed status is carried forward (“in-hospital outcome”). That is, if the patient is receiving invasive mechanical ventilation at hospital discharge, the analysis assumes s/he continued to receive invasive mechanical

ventilation through Study Day 29. If the patient is not receiving invasive mechanical ventilation at hospital discharge, the analysis assumes the patient continued not to receive invasive mechanical ventilation through Study Day 29.

10.9.3 Vasopressor-free days to Day 28

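### Time to recovery counts any discharge from the index hospital as recovery, even on a ventilator or shortly before death, and the primary scale leaves ventilated patients in long-term acute care unclassified

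*SAP*

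**What the plan says.** **Time to recovery (SAP 10.5).** Discharge is a route to recovery in its own right: "A patient can reach category 1, 2, or 3 on the seven-category COVID Ordinal Outcome Scale either by (a) being discharged from the hospital". No condition is set on support or destination. For someone leaving on oxygen, the date of discharge is the date of recovery ("For a patient who is receiving supplemental oxygen at the time of discharge from the index hospitalization, the time to recovery is the time" between randomization and discharge). The outcome "does not reflect information on receipt of supplemental oxygen, rehospitalization, or death after discharge from the index hospitalization". Two groups fail to recover and receive 28.0 days: patients still in hospital on oxygen 28 days after randomization, and patients who die in hospital ("All patients who die prior to discharge from the index hospitalization are not considered to have experienced recovery").

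**Support-free days (SAP 10.9).** For oxygen-free days, "supplemental oxygen is defined as oxygen administered by nasal cannula, face mask, high-flow nasal cannula, non-invasive ventilation, or invasive ventilation". SAP 10.9.2 has a rule for what happens "if the patient is receiving invasive mechanical ventilation at hospital discharge": ventilation is assumed to continue through Study Day 29. Death in any location before Study Day 29 gives zero support-free days.

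**Discharge destinations (Protocol 7.3.1).** Telephone follow-up covers patients "discharged to home or a post-acute care facility (e.g., long term acute care facilities, skilled nursing facilities, or acute rehabilitation facilities"). The location recorded at the call lists a long-term acute care facility and a hospital as separate options.

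**Primary scale (Protocol 6.1, SAP section 8).** Categories 3 to 6 all require the patient to be hospitalized. Category 2 is "Not hospitalized, but unable to resume normal activities". After discharge, SAP 3.2 discusses only how to separate category 1 from category 2, and gives category 2 to patients who are not reached unless an earlier category 1 is carried forward.

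**The concern.** Leaving the index hospital is an administrative event. For most patients it marks improvement. For a patient moved to long-term acute care after prolonged ventilation, or discharged shortly before death, it does not. SAP 10.5 treats all of these alike, so some of the sickest patients receive a recovered value instead of the worst value on the scale.

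If discharge practice is similar in the two arms, these patients come from the prolonged-ventilation group that an effective treatment would shrink. Scoring them as recovered would then flatter the worse arm and pull the estimate toward no effect. If practice differs by arm, the direction cannot be predicted.

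On the primary scale the worry is consistency. A ventilated patient in a long-term acute care facility on Study Day 15 has no stated category, and two assessors could score that patient at nearly opposite ends of the scale.

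**Working it through.** **1. Time to recovery: the rules applied to example patients.** The plan gives no figure to reproduce, so this is a reading of the text. Assume randomization and infusion on the same day, so that Study Day 15 is 14 days after randomization.

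| Patient | Time to recovery | Other outcomes |
|---|---|---|
| Ventilated since randomization; leaves ventilated for long-term acute care at 10 days; alive at Day 29 | 10 days | Ventilator-free days 0 (ventilation carried forward); Day 15 category 2 or 6, not stated |
| Same course, but stays in the index hospital and is ventilated at 28 days | 28.0 | Ventilator-free days 0; Day 15 category 6 |
| Discharged at 10 days, dies at 12 days | 10 days | Day 15 category 7 if the death is found; all support-free days 0 |
| Dies in hospital at 12 days | 28.0 | Day 15 category 7; all support-free days 0 |

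Rows 1 and 2 differ only in which building the patient is in. Rows 3 and 4 differ only in where death occurred. The result does not depend on borrowing the oxygen definition from SAP 10.9.1, because SAP 10.5 makes discharge alone sufficient.

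**2. Primary scale: possible size.** The Day 15 control distribution is not in the documents, so the following is assumed.

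- Control percentages for categories 1 to 7: 25, 30, 5, 12, 5, 11, 12.
- Treated arm: logit(cumulative probability, treated) = logit(cumulative probability, control) − ln 0.73. Category 6 becomes 8.85%.
- Expected in category 6 with 500 per arm: 500 × 0.11 + 500 × 0.0885 = 55 + 44.25, about 99.
- Move a fraction f of category 6 to category 2 in both arms and refit the proportional-odds model.

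| f | Patients moved per 1000 | Fitted odds ratio |
|---|---|---|
| 0 | 0 | 0.730 |
| 0.10 | about 10 | 0.732 |
| 0.20 | about 20 | 0.734 |
| 0.30 | about 30 | 0.736 |

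**3. Sensitivity to the assumed distribution.** Two other control distributions with 10% in category 6 were tried: A (20, 35, 8, 10, 5, 10, 12) and B (10, 40, 5, 15, 8, 10, 12). Approximate power uses:

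- z = √(2 ln 7) = 1.973 for a likelihood ratio of 7;
- variance of the log odds ratio = 12/[N(1 − Σp³)], with N = 1000 and p the category proportions averaged over the arms;
- power = Φ(|ln OR|/SE − 1.973).

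The plan's 80% power at 0.73 cannot be strictly reproduced without its control distribution. This formula returns 80% when 1 − Σp³ is about 0.96, and 79% (A) and 78% (B) here.

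| f | Odds ratio, A / B | Approximate power, A / B |
|---|---|---|
| 0 | 0.730 / 0.730 | 79% / 78% |
| 0.10 | 0.732 / 0.733 | 78% / 77% |
| 0.25 | 0.735 / 0.738 | 77% / 75% |
| 0.50 | 0.741 / 0.745 | 74% / 71% |

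No trial-level effect is computed for time to recovery, because the documents give neither its distribution nor a rate of such discharges.

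**The case against.** The best defence is that the rule is deliberate. SAP 10.5 labels time to recovery an in-hospital outcome, says what it leaves out, and cites an earlier trial. It is one of many secondary outcomes, and outcomes that measure different things may give one patient different values. This shows intent, and it is fair to say the plan discloses the rule. It does not remove the problem. Oxygen- and ventilator-free days are also labelled in-hospital outcomes, yet they carry support at discharge forward and give zero for death in any location. Time to recovery does neither.

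Three stronger readings are tempting, and the documents do not support them:

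- *A reader might infer that a ventilated long-term acute care patient is scored category 2 on the primary scale.* No text says so. The Day 15 call may be made to facility staff and covers the full scale, and nothing bars category 6. The discussion of category 1 versus 2 sits in the missing-data section. What stands is that the state is undefined.
- *A reader might infer that patients discharged to die score well on the primary outcome.* A death by Day 15 is category 7 if it is found, and the protocol plans an active search for vital status at Day 29. The exclusion of patients not committed to full support also makes such discharges less common. The favourable value is confined mainly to time to recovery and to scale readings taken before death.
- *A reader might infer that transfer to another acute hospital is recovery.* SAP 10.5 does not say that such a transfer is a discharge, and Protocol 7.3.1 names only home and post-acute facilities as destinations.

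**Conclusion.** The point holds for time to recovery on the explicit wording of SAP 10.5: a patient discharged on a ventilator, or who dies soon after discharge, is recorded as recovered. Per patient the value changes from 28.0 to the day of discharge. The number of such patients is unknown.

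For the primary outcome the finding is narrower. The status of a ventilated patient in long-term acute care is not defined, although the SAP foresees discharge on a ventilator. The likely effect is small: 0.73 becomes about 0.732-0.736 if 10-30% of category 6 is rescored. That rests on an assumed outcome distribution, an assumed rate and similar discharge practice in both arms. Even an extreme 50% gives 0.741-0.745 under distributions A and B.

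The 14- and 28-day mortality outcomes, survival, and oxygen- and ventilator-free days are not affected. This is worth correcting before unblinding because the correction is cheap, not because it threatens the primary conclusion.

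**What to change.** **(a) SAP 10.5, support.** A patient discharged from the index hospital to any facility on high-flow oxygen, non-invasive ventilation, invasive ventilation or ECMO is not recovered and receives 28.0 days. This carries support at discharge forward, as SAP 10.9.2 already does. Discharge on ordinary supplemental oxygen keeps its present rule.

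**(b) SAP 10.5, death.** A patient known to have died by Study Day 29 in any location is not recovered (28.0), in line with SAP 10.9. Keep the current in-hospital definition as a sensitivity analysis.

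**(c) SAP section 8.** A patient on such support in a long-term acute care facility or another acute hospital counts as hospitalized and is scored by the support reported at the call.

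**Cost.** Parts (a) and (b) need only a change of SAP wording: support dates up to discharge, location at the call and date of death are already collected (Protocol 7.2 and 7.3.1). Support after index discharge is not collected, which is why (a) carries the last status forward rather than asking when support stopped. Part (c) adds one respiratory-support question to the call for the few patients in such facilities. Time to recovery would no longer be purely in-hospital, and a patient weaned soon after transfer would be scored conservatively.

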10.9 Days Free of Support

For all outcomes related to days alive and free from a supportive therapy, “-free days” will be calculated as 28 minus the number of days the number of days on support. If a patient is on support for a portion of a day, the whole day is counted as a day on support. The day of randomization contributes to the count of “-free days”. Days between randomization and the first receipt of the supportive therapy and days following the last day of the support therapy both count toward the total number of “-free days”. Days alive and free of the supportive therapy that occur between periods receiving support do not count toward “-free days”. Information on organ support therapies (oxygen, ventilation, vasopressors, ICU care) are collected during the index hospitalization (“in-hospital data”) while death is collected both in-hospital and out-of-hospital to Study Day 29 (“all-location data”). Thus, patients who died at any time before Study Day 29 will be coded as having zero-free days.

10.9.1 Oxygen-free days through Day 28

For calculation of oxygen-free days, supplemental oxygen is defined as oxygen administered by nasal cannula, face mask, high-flow nasal cannula, non-invasive ventilation, or invasive ventilation. Positive airway pressure (CPAP, BiPAP) provided solely at night as treatment for sleep-disordered breathing (e.g. obstructive sleep apnea) is not considered supplemental oxygen. Oxygen-free days are calculated as the number of whole calendar days alive and not receiving supplemental oxygen between randomization and study day 29. Patients who die before Day 29 receive a value of 0. If a patient survives through study day 29 and never receives supplemental oxygen, the number of oxygen-free days is 28. If a patient receives supplemental oxygen and survives through study day 28, the number of oxygen free-days is calculated as 28 minus the number of calendar days from the first day on which the patient receives supplemental oxygen until the last day on which the patient receives supplemental oxygen. Days on which the patient does not receive supplemental oxygen that occur between days on which the patient receives supplemental oxygen do not count towards the number of oxygen free days. Data on oxygen use are censored at hospital discharge and the last observed status will be carried forward (“in-hospital outcome”). That is, if the patient is receiving supplemental oxygen at hospital discharge, the analysis assumes they continue to receive supplemental oxygen through Study Day 29. If the patient is not receiving supplemental oxygen at hospital discharge, the analysis assumes the patient continues not to receive supplemental oxygen through Study Day 29.

10.9.2 Ventilator-free days to Day 28

Ventilator-free days to day 28 is defined as the number of whole calendar days alive and breathing without invasive mechanical ventilation from 00:00 on the day of randomization through Study Day 29. Patients who die before Study Day 29 receive a value of 0. If a patient survives to the first of discharge or Study Day 29 and never receives invasive mechanical ventilation, the number of VFDs is 28. If a patient receives invasive mechanical ventilation and survives to the first of hospital discharge or Study Day 28, the number of VFDs is calculated as 28 minus the number of calendar days from the first day on which the patient received invasive mechanical ventilation until the last day on which the patient received invasive mechanical ventilation. Days on which the patient does not receive invasive mechanical ventilation that occur between days on which the patient did receive mechanical ventilation do not count towards the number of VFDs. Data on ventilation are censored at hospital discharge and the last observed status is carried forward (“in-hospital outcome”). That is, if the patient is receiving invasive mechanical ventilation at hospital discharge, the analysis assumes s/he continued to receive invasive mechanical

ventilation through Study Day 29. If the patient is not receiving invasive mechanical ventilation at hospital discharge, the analysis assumes the patient continued not to receive invasive mechanical ventilation through Study Day 29.

10.9.3 Vasopressor-free days to Day 28

For vasopressor-free days, a day on which a patient received of any of the following medications via intravenous drip or push at any dose is considered a day receiving vasopressors: norepinephrine, epinephrine, vasopressin, phenylephrine, angiotensin II, dobutamine, or dopamine. Vasopressor-free days to Day 28 is calculated as the number of whole calendar days alive and not receiving intravenous vasopressors or inotropes from 00:00 on the day of randomization through study day 29. Patients who die before Study Day 29 receive a value of 0. If a patient survives to Study Day 29 and never receives intravenous vasopressors or inotropes, the number of vasopressor-free days is 28. If a patient receives intravenous vasopressors or inotropes and survives to the first of discharge or Study Day 29, the number of vasopressor-free days was calculated as 28 minus the number of calendar days from the first day on which the patient received vasopressors or inotropes until the last day on which the patient received vasopressors or inotropes. Days on which the patient did not receive vasopressors or inotropes that occurred between days on which the patient received vasopressors or inotropes do not count towards the number of vasopressor-free days. Data on vasopressor use is censored at hospital discharge and the last observed status is carried forward (“in-hospital outcome”). That is, if the patient is known to be receiving vasopressors or inotropes at hospital discharge, the analysis assumes he/she continued to receive vasopressors or inotropes through Study Day 29. If the patient was not receiving vasopressors or inotropes at hospital discharge, the analysis assumes the patient continued not to receive vasopressors or inotropes through Study Day 29.

10.9.4 ICU-free days to Day 28

Intensive care unit-free days (ICU-free days) to day 28 is defined as the number of whole calendar days alive and not admitted to an intensive care unit from 00:00 on the day of randomization through Study Day 29. Patients who die before Study Day 29 receive a value of 0. If a patient survives to the first of discharge or Study Day 29 and is never admitted to an ICU, the number of ICU-free days is 28. If a patient is admitted to an ICU and survives to the first of discharge or Study Day 28, the number of ICU-free days is calculated as 28 minus the number of calendar days from the first ICU admission to final ICU discharge. Days on which the patient was not admitted to an ICU that occurred between days on which the patient was admitted to an ICU do not count towards the number of ICU-free days. Data on ICU use is censored at hospital discharge and the last observed status is carried forward (“in-hospital outcome”). That is, the analysis assumes that a patient who was discharge from the index hospitalization was not readmitted to an ICU between hospital discharge and Study Day 29.

10.9.5 Hospital-free days to Day 28

Hospital-free days to Day 28 is defined as the number of whole calendar days on which the patient was alive and not in the hospital from 00:00 on the day of randomization through Study Day 29. Patients who die before Study Day 29 receive a value of 0. If a patient remains in the hospital during the index hospitalization through Study Day 29, the number of hospital-free days is 0. For patients discharged from the index hospitalization prior to Study Day 28, the number of hospital-free days is calculated as 28 minus the duration of the index hospitalization in calendar days. Readmissions occurring after discharge from the index hospitalization do not contribute to the calculation of the hospital-free days outcome.

11 Definition of Safety Outcomes

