5. STUDY INTERVENTIONS

5.1 Treatment of Study Participants

A summary of the trial's schedule of events is included in Appendix A.

Timing of study procedures is based on the time of initiation of the study product infusion, which is defined as "Time 0". Study Day 1 is defined as the calendar day of study product infusion. For patients who are randomized but do not receive study product, time of randomization will be considered "Time 0" and Study 1 will be the calendar day of randomization. For most patients, randomization and study product infusion will occur on the same day; in the event the study product is infused on a different calendar day than randomization, Study Day 1 is defined as the day on which study product is infused. "Baseline status" represents the patient's status immediately prior to study infusion, and baseline variables should represent information available before and as close as possible to initiation of the study infusion. The primary outcome will be assessed on Study Day 15 which corresponds to 2 weeks (14 days) after the receipt of the study infusion.

Transfusion of convalescent plasma or placebo will be administered as a single dose by clinical or research personnel while the patient is hospitalized and within 24 hours of randomization. Participants randomized to active treatment will receive 1 unit of convalescent plasma, which has a volume of 200-399 ml infused intravenously. Patients randomized to placebo will receive 250 ml of lactated Ringer's with multivitamin additives infused intravenously. The duration of infusion is recommended to be between approximately 1 hour and 3 hours (at the discretion of the provider), with the specific rate of infusion determined by the site investigator based on an assessment of how quickly the participant can safely receive the intravascular volume load.

Study personnel will monitor patients for adverse reactions to the transfusion while the patient is in the hospital for 72 hours following the infusion; that is transfusion adverse reaction monitoring will be continued until Study

Day 4. For patients who are discharged prior to Day 4, study personnel will obtain safety outcomes from the patient or surrogate via telephone follow-up scheduled at Day 8. Research personnel will also assess patients at Day 15 and Day 29; these assessments will be completed by phone if the patient has been discharged from the hospital.

Screening, consent, and baseline

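### Two SAP derivation rules fail as written: every discharge before day 28 is recorded as day 28, and survivors on support throughout score below the dead

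*SAP*

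**What the plan says.** Protocol section 6 leaves outcome definitions to the SAP, so the SAP wording governs.

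**Time to discharge.** SAP 10.4 states: "The count of days after randomization until discharge from the index hospitalization occurs, or day 28, whichever is longer, will be recorded". It then makes death a competing risk. The SAP section 6 table lists this outcome as time-to-event through 28 days, analysed with a multistate model.

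**Support-free days.** SAP 10.9 subtracts days on support from 28 and counts any part-day as a whole day. For oxygen, 10.9.1 has this rule: "the number of oxygen free-days is calculated as 28 minus the number of calendar days from the first day on which the patient receives". The count ends on the last day of oxygen. Status at discharge is carried forward: "if the patient is receiving supplemental oxygen at hospital discharge, the analysis assumes they continue to receive supplemental oxygen through Study Day 29". Sections 10.9.2 and 10.9.3 have the same subtraction and carry-forward. Section 10.9.4 has the same subtraction for ICU stay but assumes no ICU readmission after discharge. Deaths get 0: "patients who died at any time before Study Day 29 will be coded as having zero-free days".

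**The window.** SAP 10.9.3 gives this definition: "number of whole calendar days alive and not receiving intravenous vasopressors or inotropes from 00:00 on the day of randomization through study day 29". Sections 10.9.2 and 10.9.4 use the same window. Yet 10.9.3 also says: "If a patient survives to Study Day 29 and never receives intravenous vasopressors or inotropes, the number of vasopressor-free days is 28".

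**Day numbering.** SAP 10.8 places Study Day 29 at 28 days after randomization. Protocol 5.1 ties Study Day 1 to the infusion when it falls on a different date from randomization: "Study Day 1 is defined as the day on which study product is infused".

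**The concern.** Taking the later of two days in 10.4 removes all timing information inside the 28-day horizon and keeps values beyond it. That is the reverse of what a time-to-discharge outcome through 28 days needs.

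For the support-free outcomes, a 29-day window is subtracted from 28 and nothing stops the result at 0. SAP 6.1 analyses these outcomes with the same cumulative probability model as the primary endpoint, where only the order of values counts. A score of −1 therefore ranks a survivor on continuous support below a patient who died. For oxygen this needs no month-long stay, because the carry-forward fills the remaining days after discharge. A treatment that turned deaths into discharges on oxygen would be scored as harmful on this outcome.

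**Working it through.** **1. Time to discharge (10.4).** As written, the recorded value is max(t, 28), where t is the discharge day. The intended value appears to be min(t, 28), with patients still in hospital censored at 28.

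| t | As written | Earlier of the two |
|---|---|---|
| 3 | 28 | 3 |
| 7 | 28 | 7 |
| 20 | 28 | 20 |
| 27 | 28 | 27 |
| 35 | 35 | 28 (censored) |

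As written, discharge days 1 to 28 share one value; they should give 28 distinct values.

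**2. Support-free days (10.9 to 10.9.4).** Because part-days count whole, days on support are last − first + 1, and the score is 28 − (last − first + 1). With no support the score is 28 − 0 = 28, which reproduces the SAP's stated value. The worded definition instead counts free days from Day 1 through Day 29, a window of 29 days.

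| Support | SAP formula | Worded definition |
|---|---|---|
| None | 28 | 29 |
| Days 1–5 | 28 − 5 = 23 | 29 − 5 = 24 |
| Days 1–28 | 28 − 28 = 0 | 29 − 28 = 1 |
| Days 1–29 | 28 − 29 = −1 | 29 − 29 = 0 |
| Death | 0 | 0 |

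The two disagree by one day in every row for survivors. A survivor on oxygen on Day 1 and discharged on oxygen on Day 4 (or 6, 10 or 20) is treated as on oxygen for Days 1–29 and scores −1.

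If infusion falls on the calendar day after randomization, which Protocol 5.1 allows, the period from the day of randomization through Study Day 29 has 30 days. The minimum is then 28 − 30 = −2.

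Counting last − first instead would give 28 − 28 = 0 for Days 1–29. It would also give 28 for one day of support, the same as for a patient never supported, against the whole-day rule in 10.9.

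**3. Effect on the oxygen-free days estimate.** The documents give no rate of discharge on oxygen, so every input here is an assumption: 500 per arm, deaths 15% on control and 10% on plasma, a control share discharged on oxygen since Day 1 of 5% to 20%, and the other survivors in four equal positive categories. A proportional-odds model was fitted to the expected counts. An odds ratio above 1 means more oxygen-free days on plasma. The likelihood ratio (LR) compares the best-fitting effect with no effect.

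*All averted deaths become discharges on oxygen.* With a 5% control share, control is 5% at −1, 15% dead and 80% higher; plasma is 10%, 10% and 80%. With a floor at 0, both arms have 20% at 0 and 80% higher, so the odds ratio is 1.000.

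| Control share on oxygen | OR as written | OR with floor | LR as written |
|---|---|---|---|
| 5% | 0.969 | 1.000 | 1.04 |
| 10% | 0.962 | 1.000 | 1.06 |
| 15% | 0.955 | 1.000 | 1.09 |
| 20% | 0.947 | 1.000 | 1.13 |

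With deaths falling by 3 points instead of 5, the odds ratio is 0.982 to 0.968 as written and again 1.000 with a floor.

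*Averted deaths spread over survivor categories in proportion.* With the 5-point fall, the odds ratio is 1.147 to 1.085 as written, against 1.159 to 1.129 with a floor. The benefit is diluted but not reversed.

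**The case against.** The best reply is that both problems are drafting slips that the context corrects. The title of 10.4, the 28-day horizon and the multistate model all show that the earlier day was meant, and discharge dates are collected (Protocol 7.2). The support-free outcomes are worded as counts of days, which cannot be negative; the titles say Day 28; some sentences refer to survival through Day 28; and hospital-free days (10.9.5) has an explicit 0.

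The intent behind 10.4 is indeed fairly clear, but the governing text is still wrong and no correct version stands elsewhere. For the support-free days the context does not settle the matter. The worded count gives 29 for a patient never on vasopressors, where the SAP assigns 28, so definition and formula cannot both be followed. The explicit 0 in 10.9.5 has no counterpart for survivors in the other four outcomes.

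Three limits do stand:

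- **The −2 is conditional.** The SAP equates Study Day 29 with 28 days after randomization, and on that anchor the minimum is −1. The −2 arises under Protocol 5.1, the only place that defines Study Day 1.
- **Reach is uneven.** Only oxygen readily reaches −1 without a month of support. ICU-free days needs an ICU stay spanning Days 1–29.
- **The reversal depends on its assumption.** The odds ratio falls below 1 when all averted deaths become discharges on oxygen. When they are spread proportionally, the error only weakens the estimate.

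**Conclusion.** Both rules are wrong as written and should be corrected. The recording and scoring errors follow from the SAP text alone, apart from the −2 case, which also needs Protocol 5.1. The size of any bias does not: it depends on how many survivors are on support throughout or go home on oxygen, which the documents do not say. In the illustrations the oxygen-free days odds ratio moves by about 1% to 5%, and in the unfavourable case the likelihood ratio stays at or below 1.13, far from the threshold of 7. The literal time-to-discharge variable is unusable and would have to be re-derived from the discharge dates. The problem is confined to five secondary outcomes; the primary outcome, the mortality stopping rule, the sample size and the power are untouched.

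**What to change.** - **10.4:** record the earlier of discharge and day 28, censor patients still in hospital at day 28, and keep death as a competing risk.
- **10.9 to 10.9.4:** count support over one window of 28 calendar days with one stated start, for example the day of randomization plus the next 27 days. End the definitions and the carry-forward at the close of that window instead of at Study Day 29, and set a minimum of 0 for survivors. A separate lower code for death is optional and is a design choice.
- **Wording to align in the same edit:** in 10.9.5, count hospital days from the day of randomization. In 10.9.2 to 10.9.4, remove discharge as an alternative endpoint for survival. For example, "If a patient survives to the first of discharge or Study Day 29 and never receives invasive mechanical ventilation, the number of VFDs is 28" can be read as giving 28 to a patient who dies after discharge, whereas 10.9 gives that patient 0.

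The cost is a few SAP sentences. No new data are needed, since the support, discharge and death dates are already collected under Protocol 7.2 and 7.3.1.
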